### **9.3.1.1 MS diagnosis and Exposures**

#### **MS Registers (SWE, NOR)**

Information on MS diagnoses will be obtained from MS registers in SWE and NOR. The Norwegian MS Register was established in 1998 (Myhr et al. 2012). In 2012, the register included information on more than 5000 patients regarding demographics, diagnosis, disease modifying treatment and follow-up, as well as disease activity with clinical scoring and several patient-reported outcome measures. The register includes also information on patients' comorbidity, co-medication, and siblings with MS. During 2007 the registry was expanded to include a biobank for collection of blood samples (DNA and serum).

The Swedish MS Register was officially launched in 2001 and contains data since 1996. Since 2011 the register has been part of the Swedish Neuro Register. The register is a nationwide quality registry for patients diagnosed with MS. Most MS specialists in SWE use the Swedish MS Register to enter information on age at onset and sex as well as clinical parameters, such as disease course, relapses, and treatment. The register dates back to 2002 and contains mostly prospective cases, although some clinics have entered data retrospectively.

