cladribine	L01BB04	no	25.9.2000	19.11.1993	14.11.1996	injection no infusion yes
mitoxantrone	L01DB07	no	30.8.1993	29.10.1987	1.8.1988	yes
alemtuzumab	L01XC04	no	12.9.2013	no	no	yes
glatimer acetate (Copaxone ® )	L03AX13	yes	8.3.2004	21.9.2001	24.2.2004	no 
leflunomide	L04AA13	yes	2.9.1999	2.9.1999	5.11.2004	no
natalizumab	L04AA23	no	27.6.2006	27.6.2006	27.6.2006	yes
fingolimod	L04AA27	yes	17.3.2011	17.3.2011	17.3.2011	no
teriflunomide	L04AA31	yes	26.8.2013	26.8.2013	26.8.2013	no
azathioprine	L04AX01	yes	31.1.1968	14.3.1968	9.8.1968	no
dimethyl fumarate	N07XX09	no	30.1.2014	30.1.2014	30.1.2014	no

-  Information on only reimbursed medication can be acquired from the National Prescription Register in Finland.
-  Pre-filled syringes/pens and tablets.
-  Injection and infusion solutions - except Trexan injection solution, which is reimbursed.
-  Information on drug use in hospitals and outpatient clinics are not collected in the Prescription Registers and thus information on exposure to these types of medication is not available.
-  Some of the injections are given in hospital and some can be self-administered at home.
-  Earlier there may have been also products that have been administered in hospital.
-  Sources (accessed on 3.2.2015):  
[http://www.ema.europa.eu/ema/index.jsp?curl=pages/medicines/landing/epar\\_search.jsp&mid=WC0b01ac058001d124](http://www.ema.europa.eu/ema/index.jsp?curl=pages/medicines/landing/epar_search.jsp&mid=WC0b01ac058001d124),  
<http://www.fimea.fi/laaketieto/valmisteyhteenvetot/laakkeet>  
<http://www.lakemedelsverket.se/LMF>  
<http://www.legemiddelverket.no/Legemiddelsoek/>

**Outcome variables:** The primary (P), secondary (S) and exploratory (E) outcomes are presented here according to pregnancy timeline.

Ectopic pregnancies (S) (ICD-10: O00) and spontaneous abortions (S) (ICD-10:O03):

- Information will be obtained from Patient Register (FIN, SWE, NOR) based on hospital visits due to these diagnoses

Elective termination of pregnancy (P) (ICD-10: O04):

- Information will be obtained from the DPP (FIN) and from MBR (NOR), where the abortions are registered from GW 12.
- This information is not available from SWE.

Stillbirth (P):

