The estimated background prevalence for the composite endpoint of serious adverse pregnancy outcome, consisting of TOPFAs, live births with MCA and all stillbirths, was 6.5% (personal communication with [name], THL, 15 May 2014) and 7.3% (= 24/331, based on the feasibility study in Finland, cf. Annex 1) in women with MS unexposed to IFN- $\beta$  (regardless of exposure to other MSDMDs) and unexposed to any MSDMD, respectively. Because these numbers best correspond to the study setting, they were taken as the most relevant baseline prevalences of serious adverse pregnancy outcomes in the sample size calculations. Lower outcome prevalences were investigated to test how sensitive the findings of minimum detectable effect sizes are to these assumptions. For comparison, in the Finnish feasibility study the prevalence of serious adverse outcomes was 3.7% = (38384/1031778) among all women, and according to EUROCAT 2015, the prevalence of malformation outcome among all women in the EU is 2.6%. The anticipated sample sizes in study cohorts 1-6 are:

- Cohort 1: 294 (80% of 368) for MS pregnancies exposed only to IFN- $\beta$ .
- Cohort 2: 368 (22% of 1671) for MS pregnancies exposed to IFN- $\beta$  regardless of exposure to other MSDMDs.
- Cohort 3: 1270 (76% of 1671) for MS pregnancies unexposed to any MSDMD.
- Cohort 4: 1303 (78% of 1671) for MS pregnancies unexposed to IFN- $\beta$ .
- Cohort 5: 33 (Cohort 4 size – Cohort 3 size = 1303 – 1270 = 33) for MS pregnancies exposed to MSDMDs except IFN- $\beta$  or glatiramer acetate (Copaxone®) or dimethyl fumarate (Tecfidera®).
- Cohort 6: Approximately 2.9 Million pregnancies for women from the general population in FIN, SWE and NOR without MS diagnosis based on the based on the feasibility study (cf. Annex 1).

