- New MS immunomodulatory therapies (e.g. cladribine, mitoxantrone and teriflunomide) can have long-term side effects. The proportion of pregnancies in different study cohorts that are using these treatments with respective treatment duration and duration of unexposed period at LMP will be reported. In addition, two separate sensitivity analyses are to be performed: 1) analysis further adjusting for a variable never vs. ever exposed to cladribine, mitoxantrone or teriflunomide as a covariate and 2) analysis adjusting for the duration of cladribine, mitoxantrone or teriflunomide treatment prior to LMP as a covariate.
- Regarding the identification of cohort 1, exposure to IFN- $\beta$  without exposure to any other MSDMD is based on drug purchase data. It is possible that individuals in this cohort have received other MSDMDs in a hospital. In addition, steroids may be given by infusion in a hospital. To account for this possibility, a sensitivity analysis will be done for primary objective #2 using only those individuals from cohort 1 who are unexposed to the proxy MSDMD/steroid hospital exposure during the pregnancy period. To do this, a proxy for the MSDMD /steroid infusion hospital exposure will be defined for cohort 1, based on diagnoses (ICD-10 codes) and all operations codes (Nomesco classification of surgical procedures (NCSP) based classification) recorded pertaining to any hospital visits during the pregnancy period.
- To investigate if cohort 5 could be a proxy for the severity of disease with impact on the pregnancy outcomes, the descriptive statistics (n, %) will be presented for each pregnancy outcome (i.e. serious pregnancy outcome, elective TOPFA, stillbirth, live birth and MCA) in women with MS exposed to other MSDMDs but not to IFN- $\beta$  or glatiramer acetate (Copaxone®) or dimethyl fumarate (Tecfidera®) before or during pregnancy. The impact of disease severity will be assessed by presenting the prevalence of the outcomes for cohort 5 versus cohort 3.

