### **Information on MS disease**

It is known that there are regional and international differences in prevalence and incidence of MS. As for information on age at MS onset, disease status, and disease severity are not available from all MS data sources of these countries, the effect of MS and MSDMDs on these pregnancy outcomes in patients with different types of MS cannot be distinguished in this study. Therefore, confounding by indication is possible.

MS is more prevalent in Northern European countries than in southern part of Europe. It is unlikely that drug-related effects are due to the prevalence of the disease, but the large study population increases the likelihood of observed rare adverse outcomes. Information on country and region will be included in the descriptive, multivariate, as well as sensitivity analyses in this study.

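### Comparing cohort 5 with cohort 3 cannot show the impact of disease severity: the cohorts differ by drug exposure by definition, and the contrast rests on about two serious outcomes

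*Protocol*

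**What the plan says.** Section 9.7.6 gives the aim as "To investigate if cohort 5 could be a proxy for the severity of disease with impact on the pregnancy outcomes". It plans counts and percentages of each outcome in cohort 5, and ends: "The impact of disease severity will be assessed by presenting the prevalence of the outcomes for cohort 5 versus cohort 3". Table 1 defines cohort 5 as women exposed to other MS disease modifying drugs (MSDMDs) but not to IFN-beta, glatiramer acetate or dimethyl fumarate, and marks it for sensitivity analysis only. Cohort 3 has no MSDMD exposure.

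Section 9.5 sizes cohort 5 as "Cohort 4 size – Cohort 3 size = 1303 – 1270 = 33" and cohort 3 as "1270 (76% of 1671) for MS pregnancies unexposed to any MSDMD".

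Section 9.3.1.1 describes the Norwegian MS Register as holding treatment and follow-up data "as well as disease activity with clinical scoring and several patient-reported outcome measures", and the Swedish one as holding "clinical parameters, such as disease course, relapses, and treatment". Table 2 names both as sources for the MS population. Section 9.9 (Information on MS disease) explains that age at onset, disease status and "disease severity are not available from all MS data sources of these countries", and concedes that confounding by indication is possible. The covariate lists in Sections 9.4, 9.7.1 and 9.7.3 contain no relapse, disability or disease-course variable.

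**The concern.** Section 7 links the decision to stop IFN-beta around pregnancy to relapse history. Disease severity is therefore a plausible confounder of cohort 1 versus cohorts 3 and 4, and Section 9.9 accepts as much. The one analysis that the protocol labels as assessing severity uses a drug-defined group as a stand-in. Read as planned, a raised prevalence in cohort 5 could be reported as a severity effect when it is a drug effect. A similar prevalence could be taken as evidence that severity does not matter when too few events exist to tell. The protocol also describes direct severity information in two registers that it already plans to use, yet no planned analysis draws on it.

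**Working it through.** **1. What differs between the cohorts.** By Table 1, MSDMD exposure separates cohort 5 from cohort 3. Severity may differ as well, but the comparison has no means of separating the two. Leflunomide (L04AA13), azathioprine (L04AX01) and methotrexate (L04AX03) are study MSDMDs in Section 9.4 and are category D drugs in Annex 3, so by the protocol's own classification a drug effect is a live explanation. No severity measure is compared between the cohorts, so the question whether cohort 5 is a proxy for severity is not answered either.

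**2. Misclassification.** Table 3 lists natalizumab, mitoxantrone and intravenous immunoglobulin, among others, as given in hospital only. Its footnote 4 says of drug use in hospitals and outpatient clinics that "thus information on exposure to these types of medication is not available". A woman treated only with such a drug appears unexposed and falls into cohort 3. Section 9.9 acknowledges this. The hospital-exposure proxy in Section 9.7.6 is defined for cohort 1 only and does not clean cohort 3.

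**3. Reproducing the plan's figures.**
- Cohort 5: 0.78 × 1671 − 0.76 × 1671 = 1303 − 1270 = 33. Reproduced.
- Minimum detectable relative risk for cohort 1 versus cohort 3 (294 versus 1270, 7.3%, 80% power, 5% two-sided, two-proportion normal formula): 1.717, against the stated 1.72. Reproduced.

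**4. Information in cohort 5 versus cohort 3.**
- Unrounded Finnish counts: (338 − 331)/433 × 1671 = 27.0 pregnancies.
- Expected serious outcomes at 7.3%: 33 × 0.073 = 2.4; 27 × 0.073 = 2.0. At 3%, the lowest prevalence considered in Section 9.5: 33 × 0.03 = 1.0.
- Probability of 0 or 1 event with 33 pregnancies at 7.3%: 30%.
- Exact 95% CI for 2/33 (6.1%): 0.7% to 20.2%. For 2/27 (7.4%): 0.9% to 24.3%.
- Cohort 3 expects 1270 × 0.073 = 93 events. With 2/33 against 93/1270, RR = 0.0606/0.0732 = 0.83. SE of log RR = √(1/2 − 1/33 + 1/93 − 1/1270) = 0.69, so the 95% CI is 0.21 to 3.22.
- The formula that reproduces 1.72 gives a minimum detectable relative risk of about 3.1 for 33 versus 1270. Power is 39% at a true relative risk of 2.

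**5. What a Swedish and Norwegian analysis would hold.** This assumes that the protocol's exposure shares apply in both countries.
- Pregnancies: 482 + 412 = 894, or 894/1671 = 53.5%. With about 70% Swedish register coverage (Section 9.3.2.1): 0.7 × 482 + 412 = 749.
- Cohort 1: 894 × 294/1671 = 157. Cohort 3: 894 × 0.76 = 679. Together 836.
- Events: 836 × 0.073 = 61, or 836 × 0.03 = 25. With 749 pregnancies, the same steps give 51 and 21.
- At one covariate per ten outcomes (Section 9.7.3), 61 events allow 6 covariates and 21 allow 2. The base model already has six, so the covariate set would have to be cut to make room for a severity term.

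**The case against.** The contrast is descriptive, is marked as sensitivity only, and opens by asking whether cohort 5 could be a proxy. No test or decision depends on it. Section 9.9 admits confounding by indication, and Section 9.7 leaves detail to a later statistical analysis plan. Time since MS diagnosis and duration of MS treatment are candidate covariates and give partial control. All of this stands and limits the harm. It does not rescue the closing sentence, which fixes a severity interpretation that the comparison cannot bear.

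The event count could move either way. The 33 still includes women exposed only to glatiramer or dimethyl fumarate, whom cohort 5 excludes, which would lower it. The Finnish counts end in 2010, while Table 3 dates fingolimod to 2011 and teriflunomide to 2013, which could raise it. So two events is an approximate figure, not an upper bound.

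A reader might infer that Annex 3 singles out cohort 5 drugs as teratogenic. It does not: category D also lists IFN-beta (L03AB07, L03AB08). The confounding by drug follows from the cohort definitions and does not depend on that list.

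The register alternative is sparse too. Completeness of the clinical data near the last menstrual period is not stated, some Swedish clinics entered data retrospectively, and Finland, the largest contributor at 777 pregnancies, drops out. The 7.3% is a Finnish figure that includes terminations for foetal anomaly, which Sweden does not record. This argues for a small model reported with caution. It does not justify leaving the data unused: Section 9.7.6 already plans an analysis restricted to Finland and Norway for another data gap.

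**Conclusion.** The concern holds in a limited form. Cohort 5 versus cohort 3 cannot isolate severity, because drug exposure differs by construction and some treated women can sit in cohort 3. It also carries about 2.0 to 2.4 serious outcomes on the protocol's own sizes at 7.3%, and about 1 at 3%. The severity conclusion in Section 9.7.6 is therefore unsupported whichever way the numbers fall.

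A reader might go further and infer that the primary relative risk is invalid, or that severity is shown to be the main confounder. The documents support neither. The contrast does not enter the primary model, the protocol says only that confounding by indication is possible, and it gives no estimate of how severity affects the composite outcome.

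The reason in Section 9.9, that severity is not available from all sources, explains why it is missing from the pooled model. It does not rule out a two-country sensitivity analysis.

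**What to change.** 1. In Section 9.7.6, keep cohort 5 versus cohort 3 as a description with exact 95% CIs, and delete the statement that it assesses the impact of severity. This costs nothing.
2. Add the pre-pregnancy severity variables described in Section 9.3.1.1 to the Swedish and Norwegian MS register requests, before the data permit applications that Section 6 schedules one month after registration.
3. Tabulate these variables, with their completeness, by cohorts 1, 3 and 4.
4. Add a Swedish and Norwegian sensitivity analysis of primary objective 2, fitted in the same women with and without one severity term (for example one relapse or clinical-score variable). Use the same reduced covariate set in both fits, within the 1:10 limit.
5. Amend Section 9.9 to match.

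The cost is a few extra register variables, work to harmonise the two countries' measures, and one more model. The result would cover at most 894 of 1671 planned pregnancies and about 21 to 61 events, depending on prevalence and coverage. It should be reported as imprecise.

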### 9.7.7 Missing data

For study variables, if a variable is totally missing from a database, it will be excluded from the analysis. If a variable is missing for only some of the patients a missing data category will be added and used in the analysis. In addition, to investigate the robustness of the variable selection procedure (section 9.7.3) to missing data, if a candidate covariate is missing from over one quarter of patients, missing values will be imputed multiple times and the variable selection re-performed using each of the complete (imputed) data sets (Wood et al. 2008). Results for models including predictors that appear in i) any, ii) at least half, and iii) all models selected using the imputed data sets will be reported as part of the sensitivity analyses (Wood et al. 2008 section 2.4.3).

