Of these pregnancies, 76% (n=1270) are estimated to be unexposed to any MSDMDs, 22% (n=368) exposed to IFN- $\beta$  regardless of exposure to other MSDMDs, and 18% (n=294) exposed to IFN- $\beta$  only. With an anticipated background rate of 7.3% for the serious adverse pregnancy outcome, the minimum detectable effect size between the study cohorts of MS women exposed to IFN- $\beta$  only vs. MS women unexposed to any MSDMDs is 1.72 in terms of relative risk (RR) with an 80% power and 5% significance level.

**Data analysis:** The individual patient-level data from each country will be pooled into a single dataset and analyses will be conducted using the pooled dataset. The study cohorts will be characterised by country of residence, university hospital district, maternal age at LMP, year of pregnancy outcome, pre-pregnancy weight, pre-pregnancy body mass index (BMI), number of previous pregnancies, number of previous abortions, smoking status during pregnancy, number of foetuses in pregnancy (single vs. multiple), any chronic diseases, exposure to any teratogenic medications including steroids, time since MS diagnosis, and duration of MS treatment. These variables are also used as potential confounders when comparing the pregnancy outcomes between the study cohorts.

The descriptive statistics including number of events (n) and prevalence (%) will be presented for each pregnancy outcome in each study cohort separately. Descriptive analyses of the pregnancy outcomes within each study cohort will be further stratified by country, year of pregnancy outcome, maternal age at LMP, any chronic diseases, exposure to any teratogenic medication including steroids, time since MS diagnosis, duration of MS treatment, gestational age, and weight of the newborn as relevant for specific pregnancy outcomes.

The prevalence of the pregnancy outcomes will be further compared between the study cohorts using log-binomial regression with adjustments for i) baseline potential confounders (country, year, maternal age at LMP, previous pregnancies, chronic diseases, exposure to teratogenic medications including steroids) and ii) all relevant confounders. The RR estimates with 95% confidence intervals (CI) and associated p-values will be reported for these comparisons and for confounders used in the model. Confounding factors will be taken into account in the analyses according to availability and available time period from each register source.

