### **9.3.1.2 Outcomes**

#### **Medical Birth Registers (FIN, SWE, NOR)**

Information on live births and stillbirths will be obtained from the MBR in each country (via DPP in FIN). Furthermore, information on abortions and MCAs will be obtained from MBR for NOR. The MBR's purpose for collecting data is to develop and organise maternity care, obstetrical services and neonatal care.

Each of the countries included in this study has kept medical birth registers for decades (established: FIN 1987, SWE 1973 and NOR 1967), with compulsory notification (Langhoff-Roos et al. 2014). All live births and stillbirths from varying gestational ages in the different countries are notified to the registers. There is some variation in content between the Nordic MBRs, but all the registers include some information on maternal socio-demographic background (e.g. marital status, age, smoking status), previous pregnancies and deliveries, maternal diagnoses (ICD-10 codes), care and interventions during pregnancy and delivery, and information on newborn health, diagnoses, care and interventions (Gissler 2010). Diagnoses are registered as ICD-8, ICD-9 and ICD-10 codes. The international origin of the codes for some main groups created through the registers allows for cross-country research on large populations within the Nordic countries. However, codes for each individual case are assigned nationally and this may involve minor differences between the countries. Birth notification forms are linked to MBRs and to population census offices.

The follow-up ends usually when the child is discharged from the hospital or, at the latest, until the end of perinatal period, i.e. the first week of living. Information on deaths, however, can cover the whole infant period until one year of age (Gissler 2010).

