### **Patient Registers (FIN, SWE, NOR)**

Information on hospitalisations due to MS, spontaneous abortions, and ectopic pregnancies will be obtained from the Patient Registers in this study. The Patient Register includes individual-level inpatient data in FIN SWE and NOR (established: FIN 1969, SWE 1987, NOR 2008). Outpatient visits are available since 1998 in FIN, 2001 in SWE and 2008 in NOR. The registers include data on hospitalisations with information on diagnosis (ICD-10), start and end date of the hospitalisation period, operations and other procedures performed, and identification of the hospital and the hospital district. In addition, outpatient visits in the secondary healthcare units and day surgeries are included the registers. No primary care data are currently available.

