### Spontaneous abortions and ectopic pregnancies

Information on spontaneous abortions and ectopic pregnancies will be obtained from the Patient Register. The quality of the data of the Patient Registers is dependent on the quality of the master data that is registered by the sector. According to validity studies focused on the quality of the Swedish (Ludvigsson et al. 2011) and Finnish (Sund 2012) patient register data comparing the data to external information sources, the overall completeness and accuracy seemed to vary from satisfactory to very good in these registers. In the Finnish study more than 95% of discharges could be identified from the register (Sund 2012). The positive predictive value (PPV) for common diagnoses was between 75-99% (Sund 2012). Correspondingly, the PPV varied between the diagnoses, but was generally between 85-95% in the Swedish study (Ludvigsson et al. 2011). No specific validity studies have been conducted regarding information on maternal diagnoses of spontaneous abortions or ectopic pregnancies included in the Patient Registers.

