## 9.7 Data analysis

The individual patient-level data from each country will be pooled into a single dataset and analyses will be done using the pooled dataset.

EPID Research will perform all statistical analyses by using the R programming language (<http://www.r-project.org>). Described below is the analysis strategy. A separate detailed statistical analysis plan will be written after approval of the study protocol.

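### Secondary objective 4: if the missing-category rule and the adjusted model are applied to spontaneous abortion and ectopic pregnancy, the missing level is largely defined by the outcome and biases the adjusted RR

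*Protocol*

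**What the plan says.** All references are to the Protocol.

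- **Source of the events.** Section 9.3.2.2: "Information on spontaneous abortions and ectopic pregnancies will be obtained from the Patient Register". Table 2 and section 9.4 agree for all three countries. For that register, section 9.3.1.2 states: "The registers include data on hospitalisations with information on diagnosis (ICD-10), start and end date of the hospitalisation period", and adds procedures and hospital identifiers. No smoking status or obstetric history is listed.
- **Source of the covariates.** The Medical Birth Registers are described in section 9.3.1.2 as holding "maternal socio-demographic background (e.g. marital status, age, smoking status), previous pregnancies and deliveries". No source is named for pre-pregnancy weight or BMI.
- **Denominator and pooling.** Table 6 divides spontaneous abortions and ectopic pregnancies by all pregnancy events. Section 9.7: "The individual patient-level data from each country will be pooled into a single dataset".
- **Model.** The abstract states: "The prevalence of the pregnancy outcomes will be further compared between the study cohorts using log-binomial regression with adjustments for" baseline confounders and then all relevant confounders. Section 9.7.4 says for objective 4 only that the prevalences will be compared. Section 9.7.3 puts number of previous pregnancies in the base model. Smoking, weight, BMI, previous abortions and number of foetuses are candidates for the adjusted model.
- **Missing data.** Section 9.7.7: "If a variable is missing for only some of the patients a missing data category will be added and used in the analysis". The sentence before it says "if a variable is totally missing from a database, it will be excluded from the analysis", and a later one says "if a candidate covariate is missing from over one quarter of patients, missing values will be imputed multiple times".

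**The concern.** A spontaneous abortion or ectopic pregnancy enters the data without the birth-register variables; a birth normally enters with them. In the pooled file such a variable is missing for only some pregnancies, which is the stated trigger for a missing category. That category then holds nearly all the events and few of the non-events. Adjusting for it means comparing exposed and unexposed pregnancies mainly within a group selected by the outcome.

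This matters because section 7 names a possible increased risk of spontaneous abortion, and section 9.9 says that cohort differences in this outcome are likely to reflect exposure. A real difference could shrink on adjustment for reasons unrelated to confounding.

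**Working it through.** **The plan's own figure.** The only stated figure on pregnancies that end without a birth record is Norwegian: 330 births / (1 − 0.2) = 412.5, given as 412 (section 9.5, Table 5). It reproduces and is not contested. It motivates a total loss share of about 20% below.

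**Inputs.** From section 9.5: cohort 1 = 294, cohort 3 = 1270. Assumed, because the protocol does not give them: rates of spontaneous abortion (SA), ectopic pregnancy (EP) and termination, and the share of births or terminations lacking the covariate. No true confounding is assumed, so an unbiased adjusted RR would equal the true RR.

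**Formula.** If no SA or EP record carries the covariate, every known-value stratum has zero events, and the log-binomial estimate is the RR inside the missing stratum:

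RR_adj = [S1/(S1 + E1 + T1 + m·B1)] / [S0/(S0 + E0 + T0 + m·B0)]

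Here S, E and B are SA, EP and births per 100 pregnancies, T is terminations lacking the covariate, and m is the share of births lacking it; 1 = exposed, 0 = unexposed.

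**Spontaneous abortion, true RR 1.5, EP RR 1**

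| Assumptions (unexposed rates) | Exposed | Unexposed | RR_adj |
|---|---|---|---|
| SA 20%, no EP | 30/30 | 20/20 | 1.00 |
| SA 18%, EP 2% | 27/29 = 0.931 | 18/20 = 0.900 | 1.03 |
| SA 10%, EP 2% | 15/17 = 0.882 | 10/12 = 0.833 | 1.06 |
| SA 18%, EP 2%, 5% of births missing | 27/32.55 = 0.829 | 18/24 = 0.750 | 1.11 |
| same, 10% of births missing | 27/36.1 = 0.748 | 18/28 = 0.643 | 1.16 |
| same, 20% of births missing | 27/43.2 = 0.625 | 18/36 = 0.500 | 1.25 |
| SA 18%, EP 2%, terminations 10%, all missing | 27/39 = 0.692 | 18/30 = 0.600 | 1.15 |
| SA 10%, EP 2%, terminations 10%, all missing | 15/27 = 0.556 | 10/22 = 0.455 | 1.22 |

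If 30% or 50% of the SA/EP covariate values are recovered from other records (SA 18%, EP 2%, 5% of births missing), the fitted values are 1.17 and 1.24. With SA 18%, EP 2% and complete births, a true RR of 2.0 gives (36/38)/0.900 = 1.05, a true 0.67 gives (12.06/14.06)/0.900 = 0.95, and a true 1.0 stays at 1.0.

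**Simulation check.** 300 datasets per setting (SA 18%, EP 2%) gave median adjusted RRs of 1.03, 1.10 and 1.16 with 0, 5 and 10% of births missing, against crude medians of 1.48, 1.50 and 1.49.

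**Ectopic pregnancy, SA 18%, EP 2%, births complete**

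| True EP RR | SA RR | Exposed | Unexposed | RR_adj |
|---|---|---|---|---|
| 1.5 | 1.5 | 3/30 = 0.100 | 2/20 = 0.100 | 1.00 |
| 1.5 | 1.0 | 3/21 = 0.143 | 0.100 | 1.43 |
| 1.0 | 1.5 | 2/29 = 0.069 | 0.100 | 0.69 |
| 1.2 | 1.5 | 2.4/29.4 = 0.082 | 0.100 | 0.82 |

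The estimate has become the ectopic share of all losses, so its direction depends on the SA effect.

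**Would variable selection remove it?** In the simulations the step 1 Wald P-value was about 0.999 because of separation, but the likelihood-ratio P-value was below 1e-170. If the procedure in 9.7.3 is rerun for SA, step 2 brings the variable back at P<0.1.

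**Would imputation repair it?** With SA 18%, EP 2% and complete births, the missing share is (294 × 0.29 + 1270 × 0.20)/1564 = 21.7%. Across the scenarios where only SA and EP lack the covariate and the SA RR is above 1, it is about 13 to 23%, below the one-quarter trigger. It can pass the trigger when births or terminations also lack values. Even then, imputation only re-tests variable selection, and it has few or no observed values among the events.

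**The case against.** The strongest reply is that the protocol does not clearly fix this analysis.

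- Section 9.7.7 excludes a variable that is wholly missing from a database. If the Patient Register counts as a database, smoking is already out. Sections 9.4 and 9.7.1 use confounders according to availability in each register source. **This stands as an ambiguity.** None of these clauses mentions objective 4, and in the pooled file the variable is missing for only some pregnancies.
- Section 9.7.4 refers back to the primary analysis for objective 3 but not for objective 4, and step 1 of the selection names the serious adverse pregnancy outcome. Only the abstract extends base and adjusted models to the pregnancy outcomes generally. A separate analysis plan, not seen here, may settle it. **This stands**, so the point is conditional.
- A reader might infer that both RRs are always pulled towards 1. That holds for SA in every scenario tried with a true effect; it fails for ectopic pregnancy.
- A reader might infer that the base model is biased too. It is affected only if number of previous pregnancies is read from the current pregnancy's birth record. Linkage by personal identifier makes rebuilding it feasible, and Table 2 notes some earlier losses in the Finnish and Norwegian sources.
- A reader might infer that a signal would vanish from the report. Cohort counts and percentages are reported, and if 9.7.3 is followed so are the base model and the effect of adding each variable. A fall between models would be visible, though it could be misread as confounding being removed.
- That weight, BMI and number of foetuses are absent for these events is inferred. Smoking and obstetric history are enough for the point.

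**Conclusion.** The point holds in conditional form. If the abstract's adjusted model and the missing-category rule are applied to objective 4, the missing level is largely defined by the outcome. A true spontaneous-abortion RR of 1.5 would then be reported as about 1.0 to 1.25. The ectopic-pregnancy RR is biased in an unpredictable direction and can cross 1, and separation or non-convergence is likely. The sizes rest on assumed event and missingness rates and on no true confounding. The mechanism rests on the register contents as the protocol lists them.

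The documents do not support saying that the protocol unambiguously orders this analysis, or that the primary composite is compromised: its denominator excludes spontaneous abortions and ectopic pregnancies. Objective 4 is secondary and subject to data availability. The wording should nevertheless be settled, since section 9.9 deals with this kind of outcome-dependent gap only for maternal age at LMP.

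**What to change.** State in 9.7.4 and 9.7.7 that models for spontaneous abortion and ectopic pregnancy use only covariates ascertainable for every pregnancy event regardless of its outcome. These are country, year, maternal age, chronic diseases, co-medication, time since MS diagnosis, duration of MS treatment, and previous pregnancies rebuilt from linked earlier records. Add that no missing category is used where missingness follows from the outcome's source register.

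The cost is a sentence or two and the derivation of pregnancy history by linkage. Smoking, weight and BMI remain unadjusted for these two outcomes, but a missing category does not adjust for them among the events either. The rule should not be extended automatically to the primary composite, where it could remove useful covariates.
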